2. STUDY OBJECTIVES AND ENDPOINTS

2.1. Stage 1, Objectives and Endpoints

Pri	mary Objective(s):	Primary Endpoint(s):						
•	To evaluate the efficacy of PF-06823859 in adult participants with moderate to severe DM.	• Change from baseline in CDASI activity score at Week 12.						
Sec	condary Objective(s):	Secondary Endpoint(s):						
•	To evaluate the efficacy of PF-06823859 over time.	• Absolute values and change from baseline of CDASI activity and CDASI damage scores at all scheduled time points. (Exception: The change from baseline in CDASI activity score at Week 12 is a primary endpoint).						
•	To determine the safety, and tolerability, of PF-06823859.	• Incidence of adverse events (AEs) laboratory abnormalities, changes in vital signs, and electrocardiogram (ECG) findings.						
Ex	ploratory Objectives (s)	Exploratory Endpoints(s)						
•	To characterize pharmacokinetics (PK) of PF-06823859.	Plasma concentration of PF-06823859.						
•	To characterize pharmacodynamics (PD) effects of PF-06823859. To evaluate the effects of PF-06823859 on patient-reported outcomes (PROs) and physician global assessment (PhGA, VAS) over time.	 Absolute values and change from baseline in the values of selected biomarkers (Gene signature panel in blood and tissue; Human Myxovirus A (MXA), interferon gamma-induced protein 10 (IP-10), CCI highly sensitive C-reactive protein, (hsCRP), muscle and bone blood biomarkers, autoantibody concentrations in serum/plasma) at all scheduled time points. Absolute values and change from baseline in the values of the PhGA, VAS, PROs (the short form (SF36) Health Survey, Dermatology and Life Quality Index (DLQI), 5D Pruritus Scale, at all scheduled time points. 						
•	To evaluate the effects of PF-06823859 on CDASI sub-scores.	 Absolute values and change from baseline values of the sub-scores of CDASI activity and CDASI damage scores at all scheduled time points. 						

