5.2. Breaking the Blind

This study will be double blinded, (Sponsor, Investigator and participant will all be and remain blinded throughout the duration of the study). An interim analysis may be conducted for internal decision making. An internal review committee, (IRC) separate from the blinded study team will review safety and efficacy data.

At the initiation of the study, the investigator site will be instructed on the method for breaking the blind. The method will be an electronic process. Blinding codes are able to be broken in exceptional circumstances when knowledge of the actual treatment code is absolutely essential for further management of the participant. If the situation allows, investigators are encouraged to discuss with the sponsor's medical monitor if they believe unblinding is necessary, however, under no circumstances should unblinding be delayed in an emergency situation. When the blinding code is broken, the reason must be fully documented and entered on the case report form (CRF).

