9.2. Efficacy Analysis

The primary efficacy analysis of Stage 1 and Stage 2 is based on the CDASI activity scores at Week 12. The primary efficacy analysis in Stage 3 is based on the TIS at Week 12. Analysis of efficacy endpoints will be performed for the modified intenttotreat (mITT) population, defined as all randomized participants who receive at least 1 dose of investigational product. Formal statistical testing for efficacy will be based on Stage 1 data only.

All treatment periods in this study will be conducted in a double blinded fashion. During this period, the participants, investigators and sponsor (or designee) will be blinded to randomized study treatments. After the treatment period is completed for all the participants, some members of the study team will be unblinded so that a report for the corresponding data can be generated. The participants, investigators, and individuals from the sponsor (or designee) who interact with the investigators and monitor safety will continue to be blinded to individual study treatments throughout the follow up period of the study. The official database release will occur after the last participant completes the last visit. The Clinical Study Report (CSR) will be based on the data generated following the database release.

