- Absolute values and change from baseline in the values of selected biomarkers (Gene signature panel in blood and tissue; Human Myxovirus A (MXA), interferon gamma-induced protein 10 (IP-10), IFNbeta, high sensitive C-reactive protein, (hsCRP), muscle and bone blood biomarkers, autoantibody concentrations in serum/plasma) at all scheduled time points.
- Absolute values and change from baseline in the values of PROs (the short form (SF36) Health Survey, Dermatology and Life Quality Index (DLQI), 5D Itch Scale, and physician's evaluation of disease (PhGA)) at all scheduled time points. The brief description of the scales is presented in Section 9.4.
- Absolute values and change from baseline values of the sub-scores of CDASI activity and CDASI damage scores at all scheduled time points. The description on the scores is presented in Section 9.2.

3.2. Endpoints in Stage 2

3.2.1. Primary Endpoint in Stage 2

• Change from baseline in CDASI activity score at Week 12.

3.2.2. Secondary Endpoints in Stage 2

- Absolute values and change from baseline of CDASI activity and CDASI damage scores at all scheduled times points. (Exception: The change from baseline in CDASI activity score at Week 12 is a primary endpoint).
- Incidence of adverse events (AEs) laboratory abnormalities, changes in vital signs, and electrocardiogram (ECG) findings. The extended discussion of these endpoints is presented in Section 9.3.

CCI

- Absolute values and change from baseline in the values of selected biomarkers (Gene signature panel in blood and tissue; Human Myxovirus A (MXA), interferon gamma-induced protein 10 (IP-10), IFNbeta, high sensitive C-reactive protein, (hsCRP), muscle and bone blood biomarkers, autoantibody concentrations in serum/plasma) at all scheduled time points.
- Absolute values and change from baseline in the values of PROs (the short form (SF36) Health Survey, Dermatology and Life Quality Index (DLQI), 5D Itch Scale, and physician's evaluation of disease (PhGA)) at all scheduled time points. The brief description of the scales is presented in Section 9.4.
- Absolute values and change from baseline values of the sub-scores of CDASI activity and CDASI damage scores at all scheduled time points. The description on the scores is presented in Section 9.2.

3.3. Endpoints in Amended Stage 2

3.3.1. Primary Endpoint in Amended Stage 2

• Change from baseline in CDASI activity score at Week 12.

3.3.2. Secondary Endpoints in Amended Stage 2

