6. ANALYSES AND SUMMARIES

6.1. Analyses and Summaries During Stage 1

6.1.1. Primary Endpoint in Stage 1

The primary endpoint is the change from baseline in CDASI activity score at Week 12.

6.1.1.1. Primary Analysis in Stage 1

- Analysis time point: Week 12.
- Analysis population: subset of FAS1 that *includes baseline observations and observations collected at weeks 1-12*. Note that subjects with some missing data are included.
- Analysis methodology: change from baseline will be analyzed using the LANCOVA-P model (as described in Section 5.2.1.1).
- Supporting objective: Primary Objective.
- Reporting results (for CDASI activity score change from baseline at Week 12):
 - The sample size, mean, standard deviation, median, minimum and maximum will be presented for each treatment arm.
 - The LS means, 90% confidence interval for the LS means, difference between the LS means of treatment groups (active-placebo) and the corresponding 90% confidence interval for the estimate. These summary statistics will also be reported for the percent change from baseline in CDASI activity score at Week 12.

6.1.1.2. Sensitivity Analyses 1-3 in Stage 1

• The sensitivity analyses will explore sensitivity of the result of the primary analysis to the following variatons of the data analysis methods (as described in Section 5.2.1) and data sets (as described in Sections 4.1.1, 4.2.1).

Table 2.	Details of Approaches to	Sensitivity Analyses of Primary	Analysis

Sensitivity Analysis	Data Set (population)	Included Observations (Time Window)	Method
1	FAS1	Baseline, weeks 1-12	LANCOVA-S
2	FAS1	Baseline, week 12	ANCOVA
3	PPAS1	Baseline, weeks 1-12	LANCOVA-S

- Here FAS1 and PPAS1 denote full and per-protocol data sets defined in Sections 4.1.1 and 4.2.1. The reporting results will include the LS means, 90% confidence interval for the LS means, difference between the LS means of treatment groups (active-placebo) and the corresponding 90% confidence interval.
- Note that in the sensitivity analyses (similarly to the primary analysis) we *do not use* data collected after Week 12 visit.
- In addition, the analysis for the CDASI-A in Section 6.1.1.1 may be repeated adjusting for subjects meeting protocol discontinuation criteria for use of prohibited medications as an intercurrent event (if any). Data from visits occurring after meeting discontinuation criteria for use of prohibited medications will be censored from this analysis.

6.1.2. Secondary Endpoint(s) in Stage 1

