7. INTERIM ANALYSES

7.1. Introduction

In Stage 1 of the study, an interim analysis was performed when 32 participants were randomized and completed Visit 6 (Week 12). Additional interim analyses during later stages of the study *may* be conducted depending on the enrollment rate. If an additional interim analysis is done in the future, an internal review committee (IRC) independent from the blinded study team will review efficacy and safety data for business decision planning, if applicable. The results of the interim analysis will not be shared with the study team, participants, or investigators.

It is expected that in addition to the study team, an unblinded team may review the (ie, any data not explicitly stated as primary or secondary endpoint) and exposure data on an ongoing basis. The analyses of the group will not be included into the report described in the current SAP.

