9.2.1. The Activity Score (AS)

The Activity Score (AS) is calculated as a sum of the contribution from the extent score (ES), Gottorn hands score (GHS), peringual score (PS) and allopecia score (AS).

$$AS = ES + GHS + PS + AS$$

The total extent score (ES) is obtained by summing up scores for the total erythema (ER, quantifies redness of the skin or mucous membranes), total scaling (SC, quantifies peeling of the skin) and total erosion/ulceration (EU, quantifies presence of the deeper wound).

$$ES = ER + SC + EU$$

Total erythema (ER), scaling (SC) and erosion/ulceration (EU) scores are calculated as a sum of the contributions from 15 individual areas of the body. The range of the total erytherma score is 0-45, the range of the total scaling score is 0-30 and the range of total erosion/ulceration is 0-15. The resulting range of the extent score is 0-90.

Gottorn hands score (GHS) characterizes papules (swellings) on hand and is a sum of the papule's characterization score (range 0-6) and ulceration score (range = 0-1).

Peringual score (PS) characterizes abnormalities around nails and its range is 0-2. The alopecia score (AS) characterizes hair loss and has the range 0-1.

The resulting range of the activity score is 0-100.

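### The ongoing unblinded review in SAP 7.1 reaches the CDASI sub-scores, which add up exactly to the primary endpoint in the skin stages

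*SAP*

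**What the plan says.** SAP 7.1 describes two unblinded routes. The first is the IRC, which is independent of the blinded study team and whose interim results go to neither the study team, participants nor investigators. Protocol 9.5.1 adds that such an interim will not alter how the study is run.

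The second is a separate unblinded team, which may review "ie, any data not explicitly stated as primary or secondary endpoint) and exposure data on an ongoing basis". On its output the SAP says only: "The analyses of the group will not be included into the report described in the current SAP".

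For the skin stages, "The primary endpoint is the change from baseline in CDASI activity score at Week 12" (SAP 6.1.1, and again in 6.2.1). The sub-scores sit elsewhere. Protocol 2.1 lists "To evaluate the effects of PF-06823859 on CDASI sub-scores" among the exploratory objectives, and 2.2 and 2.3 place them in the same class. The SAP endpoint is "Absolute values and change from baseline values of the sub-scores of CDASI activity and CDASI damage scores at all scheduled time points", which includes Week 12, and SAP 6.1.3.4 ties its analysis to the exploratory objective.

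The score itself is additive. SAP 9.2.1 begins: "The Activity Score (AS) is calculated as a sum of the contribution from the extent score (ES", and goes on to add the Gottron hands, periungual and alopecia scores. SAP 9.2.2 builds the damage score in the same way.

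On blinding, protocol 5.2 states: "Sponsor, Investigator and participant will all be and remain blinded throughout the duration of the study". Protocol 9.2 says that during treatment "the participants, investigators and sponsor (or designee) will be blinded to randomized study treatments".

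**The concern.** The bracket in SAP 7.1 is the only stated limit on what the second team may see. It works by endpoint label, not by content. A variable labelled exploratory passes through even when it is an arithmetic part of the primary endpoint. If the label does not protect the primary endpoint, nothing else written for this team does: no cap on looks, no membership, no log, no non-sharing rule and no bar on influencing conduct.

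At stake is the integrity of choices that the plan means to be made without knowledge of the arm comparison:

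- The list of major protocol deviations is to be settled before unblinding (SAP 4.2).
- The visit windows may be adjusted before unblinding, and duplicate observations within a window are assigned after consulting the study clinician and lead statistician (SAP 9.1).
- Stage 2 enrolment is given only as approximately 20 (SAP 2.2).

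Each could move the Week 12 estimates, and no text keeps the second team away from them.

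**Working it through.** **1. Are the sub-scores inside the permitted data?** The test in SAP 7.1 is whether a variable is named as a primary or secondary endpoint. In SAP 3.1 to 3.3 the primary endpoint is the change in activity score at Week 12, and the secondary endpoints are the activity and damage total scores and safety. The sub-scores are in neither list, so they pass.

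**2. Do they make up the whole activity score?** SAP 9.2.1 uses one abbreviation for both the activity score and the alopecia score; I write AL for alopecia.

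- Extent: ES = ER + SC + EU, with maxima 45 + 30 + 15 = 90.
- Gottron hands: GHS, maximum 6 + 1 = 7.
- Periungual: PS, maximum 2. Alopecia: AL, maximum 1.
- Activity score = ES + GHS + PS + AL, maximum 90 + 7 + 2 + 1 = 100.

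This reproduces the stated range of 0-100. SAP 6.1.3.4 lists every one of these terms for analysis, so nothing is left out. ES alone covers 90 of the 100 points.

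**3. Damage score.** POLS + CALS + GHDS, maximum 15 + 15 + 2 = 32, which reproduces the stated 0-32.

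**4. Does the identity carry over to the primary endpoint?** Write Δ for Week 12 minus baseline. Then for each participant

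Δactivity = ΔES + ΔGHS + ΔPS + ΔAL.

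Means are linear, so for participants with all terms observed the arm mean of Δactivity is the sum of the four arm means, and the active-minus-placebo difference is the sum of the four differences. On 1,000 simulated pairs of item-level scores, the largest gap between the summed sub-score changes and the total change was 0. With participant-level data the primary variable is recovered exactly and any planned model can be run on it.

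**5. Safeguards side by side.**

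| | IRC | Ongoing-review team |
|---|---|---|
| Results not shared | SAP 7.1, protocol 9.5.1 | not stated |
| No change to conduct | protocol 9.5.1 | not stated |
| Named in protocol 5.2 | yes | no |

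**6. Conflicting text.** Protocol 7.6.1 says that the primary and secondary endpoints assess the CDASI activity score together with its individual components. On that reading the components would be shielded. The objectives tables in protocol 2.1 to 2.3 and the endpoint lists in SAP 3 say otherwise.

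**The case against.** **Redaction.** The noun that the bracket explains is blacked out and could be narrower, for instance a class of biomarker data. This limits certainty and is not itself a fault in the plan. Even so, the visible bracket is written as the definition of the hidden word, and nothing visible excludes clinical scores.

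**Protocol 7.6.1.** Read literally, it puts the components with the primary and secondary endpoints and closes the gap. This has force, but that section is about rater training, and the sections that define endpoints class the sub-scores as exploratory. What stands is that the documents disagree on what is shielded.

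**Intent.** The sentence is permissive and plainly meant to protect the main endpoints; no passage plans to rebuild the activity score by arm. That stands. The point is a gap in a safeguard, not an allegation about what was done.

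**Other unblinded functions.** The protocol already has unblinded site preparers (5.4.2) and an analytical laboratory holding randomization codes (7.13), SAP 2 allows the SAP to modify protocol plans, and SAP 7.1 presents this team as additional to the study team. So an unblinded group is not in itself a breach. But the preparers and the laboratory do not compare clinical outcomes by arm, and a team that may do so deserves a line in protocol 5.2.

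**Conclusion.** The point holds for Stage 1, Stage 2 and Amended Stage 2. As worded, the exclusion in SAP 7.1 does not shield the CDASI activity score (primary) or damage score (secondary), because the permitted sub-scores determine both exactly. This assumes that the redacted word does not narrow the bracket and that the objectives tables, not protocol 7.6.1, settle how the sub-scores are classed. The consequence is a risk of operational bias. Its size cannot be derived from the documents, and it is nil if the looks never reach anyone making decisions.

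Three stronger readings are tempting and not supported:

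- *Inflated type I error.* Repeated looks raise the error rate only if they can trigger a decision, and no document gives this team a stopping rule. Formal testing uses Stage 1 only (protocol 9.2). Stage 1 was not cut short: 32 were randomized against about 30 planned, and the interim followed when 32 had been randomized and completed Week 12. The pooled analysis tests no hypothesis.
- *The same gap in Stage 3.* There the primary endpoint is safety, the TIS, its components and the CDASI totals are named secondary endpoints, no sub-score endpoint is listed, and no hypothesis is tested.
- *Design changes driven by this team.* Protocol 1.6 attributes the added Stage 2 dose to the disclosed IRC interim. Nothing links the ongoing-review team to it.

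**What to change.** 1. In SAP 7.1, state that CDASI total scores, sub-scores and individual items are excluded from the ongoing unblinded review, and that only the IRC may see them by arm, at a documented interim.
2. In the same section, apply to the ongoing-review team the IRC's rules: results are not shared with the study team, participants or investigators, and the review leads to no change in study conduct.
3. In protocol 5.2, name this team as an exception to sponsor blinding.
4. Reconcile protocol 7.6.1 with the objectives tables and SAP 3, so that one statement says how the CDASI components are classed.

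The cost is a few lines in each document. The exploratory team loses early sight of the clinical sub-scores but keeps the exposure and biomarker data.

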9. APPENDICES

9.1. Definition and Use of Visit Windows in Reporting

The currently assumed assignment of the observations to visits is based on the subject's arrival day. It assumes that the arrival times for each visit occur within the (-5,7) days time window centered around the target day as specified in the schedule of activities. We will check the validity of the assumption by the analysis of the visit specific, distributions of actually observed arrivival days at the end of the study before data unblinding and may update the assignment rules slightly.

Table 4. Definition and Use of Visit Windows in Reporting

Visit Label	Targeted Day	Analysis window
Screening	35 days prior to Day 1	1-35 days prior to Day 1
Baseline	Day 1 (reference day)	Day 1 (reference day)
Week 1	Day 8	Days 3-16
Week 4	Day 29	Days 24-38
Week 8	Day 57	Days 49-64
Week 12	Day 85	Days 71-99
Week 16	Day 113	Days 108-122
Week 20	Day 141	Days 136-155
Week 24	Day 169	Days 163-188
Week 28	Day 197	Days 191-218
Week 32	Day 226	Days 222-236
Week 36	Day 252	Days 245-259
Week 40	Day 280	Days 273-287

If more than one observation from the same subject falls into the same window then the association of the observation with the visit will be done after the consultation with the study clinician and lead statistician.

9.2. CDASI

Table 5. CDASI Scale

		Activity		Dama	ge	
Anatomical location	Erythema	Scale	Erosion/ Ulceration	Poikiloderma (Dyspigmentation or Telanglectasia)	Calcinosis	Anatomical location
	0-absent 1-pink; faint erythema 2-red 3-dark red	0-absent 1-scale 2-crust lichenification	0-absent 1-present	0-absent 1-present	0-absent 1-present	
Scalp						Scalp
Malar area						Malar area
Periorbital						Periorbital
Rest of the face						Rest of the face
V-area neck (frontal)						V-area neck (frontal)
Posterior neck						Posterior neck
Upper back & shoulder						Upper back & shoulds
Rest of back & buttocks						Rest of back & buttoo
Abdomen						Abdomen
Lateral upper thigh						Lateral upper thigh
Rest of leg & feet:						Rest of leg & feet
Am						Arm
Mechanic's hand						Mechanic's hand
Dorsum of hands				_		Dorsum of hands
(not over joints)						(not over joints)
Gottron's - not on hands						Gottron's - not on han
Gottron's - Hands Examine patient's hands and 0-absent 1-pink; faint erythema 2-red erythema 3-dark red		e present	Ulceration	Examine patient's I 0-absent 1-dyspigmentation 2-scarring	nands and sco	ne if damage is present
Periungual Periungual changes (examin	ne)					
0-absent	scopic telangiectasias					
2-visible telangiectasias						
2-visible telanglectasias Alopecia	30 days as reported by not	ient)				
2-visible telanglectasias Alopecia Recent Hair loss (within last	30 days as reported by par	ient)				
2-visible telanglectasias Alopecia	30 days as reported by part	ient)				

Figure 2 presents the CDASI scale. The main outcomes of interest are the activity score and damage score.

9.2.1. The Activity Score (AS)

The Activity Score (AS) is calculated as a sum of the contribution from the extent score (ES), Gottorn hands score (GHS), peringual score (PS) and allopecia score (AS).

$$AS = ES + GHS + PS + AS$$

The total extent score (ES) is obtained by summing up scores for the total erythema (ER, quantifies redness of the skin or mucous membranes), total scaling (SC, quantifies peeling of the skin) and total erosion/ulceration (EU, quantifies presence of the deeper wound).

$$ES = ER + SC + EU$$

Total erythema (ER), scaling (SC) and erosion/ulceration (EU) scores are calculated as a sum of the contributions from 15 individual areas of the body. The range of the total erytherma score is 0-45, the range of the total scaling score is 0-30 and the range of total erosion/ulceration is 0-15. The resulting range of the extent score is 0-90.

Gottorn hands score (GHS) characterizes papules (swellings) on hand and is a sum of the papule's characterization score (range 0-6) and ulceration score (range = 0-1).

Peringual score (PS) characterizes abnormalities around nails and its range is 0-2. The alopecia score (AS) characterizes hair loss and has the range 0-1.

The resulting range of the activity score is 0-100.

